7.1.2 Classification of Adverse Events

The Investigator will classify AEs based on their severity and relationship to IMP.

Every effort must be made by the Investigator to categorize each AE according to its severity (see Section 7.1.2.1 Severity) and its relationship (see Section 7.1.2.2 Relationship to Investigational Medicinal Product).

7.1.2.1 Severity

The severity of an AE will be rated by the Investigator according to the descriptions and grading scales of the Common Terminology Criteria for Adverse Events (CTCAE) (for details please refer to the integral document Terminology Criteria for Adverse Events (CTCAE, Version 4.0, published: May 28, 2009 [v4.03: June 14, 2010]); U.S. Department of Health and Human Services, National Institutes of Health, National Cancer Institute) [28], as summarized below:

Severity of AE according to CTC Grading Scale and related Guideline

- Grade 1 Mild; asymptomatic or mild symptoms; clinical or diagnostic observations only; intervention not indicated;
- Grade 2 Moderate; minimal, local or noninvasive intervention indicated; limiting age-appropriate instrumental Activities of Daily Living (ADL)*;
- Grade 3 Severe or medically significant but not immediately life-threatening; hospitalization or prolongation of hospitalization indicated; disabling; limiting self-care ADL**;
- Grade 4 Life-threatening consequences; urgent intervention indicated;
- Grade 5 Death related to AE.
- (*) Instrumental ADL refer to preparing meals, shopping for groceries or clothes, using the telephone, managing money, etc.
- (**) Self-care ADL refer to bathing, dressing and undressing, feeding self, using the toilet, taking medications, and not bedridden.

7.1.2.2 Relationship to Investigational Medicinal Product

For this trial, an AE cause and effect relationship to the study drug will be classified by the Investigator as reported hereafter.

Scale	Definition
Definitely Related	The evidence is compelling that the study drug caused the adverse event. There is a clear temporal relationship of the event to the study drug; the event is consistent with a known pattern of drug (or drug class) effects; the event cannot be explained by concurrent disease or other drugs or chemicals; the event diminished upon cessation of study drug exposure or reduction in dose; the event worsened or recurred upon unintentional re-exposure to the study drug (intentional rechallenge for the purpose of assigning causality should not be performed).
Probably Related	It is more likely that the event is due to the study drug than due to other etiologies, an alternative explanation is unlikely. There is a reasonable temporal relationship of the event to the study drug; the event may be consistent with a known pattern of drug (or drug class) effects; the drug seems more likely than other etiologies to cause the effect; the event diminished upon cessation of study drug exposure or reduction in dose.
Possibly Related	It is equally likely that the event is due to the study drug as it is due to other etiologies. There is a reasonable temporal relationship of the event to the study drug; follows a known or expected response pattern of the suspected drug but could also have been easily produced by a number of other etiologies.
Unlikely related	It is more likely that the event is due to other etiologies than due to the study drug. The event could have been reasonably related to patient's underlying diseases or concomitant treatments and/or the temporal relationship is doubtful between the study drug and the suspected adverse event.
	It the temporal relationship of the event to the study drug is reasonable, but there are important confounding factors/reasonably convincing alternative explanations, causality is considered unlikely.

Scale	Definition
Not related	The study drug almost certainly (or certainly) did not cause the event. Sufficient information exists to indicate that the etiology is unrelated to the study drug, e.g., the event is more likely related to patient's underlying diseases or concomitant treatments and/or there is no temporal relationship between the study drug and the suspected adverse event, e.g., the event occurred before the study drug was administrated.
Unassessable	The data are insufficient or contradictory to make a meaningful medical assessment.

7.1.3 Reporting of Adverse Events

AE reporting has to be in accordance with the ICH E6 Guidance on GCP and ICH E2A Guidance on Clinical Safety Management. [27, 29]

During the course of the study, all AEs (including SAEs), irrespective of the relatedness to the study drugs, will be recorded in detail in the source records and transcribed onto the AEs pages of the eCRF. During each monitoring visit, the site monitor will review all AEs and perform Source Data Verification (SDV). The investigator will be responsible for ensuring that the correct information concerning all AEs is entered on the appropriate eCRF pages.

The reporting period for AEs is the period starting from the time of Informed Consent Form signature and lasting until Visit 5 or up to 14[+3] days post-dose. All non-resolved AEs (including SAEs) beyond this date will be documented on the eCRF as "ongoing".

7.1.4 Reporting of Serious Adverse Events

All SAEs occurring from the time of signing of the Informed Consent Form/Assent until 14[+3] days post-dose must be reported immediately to the CRO Pharmacovigilance e-mail address or sent by fax (see Section General Information).

The investigator or designated study coordinator must transmit the completed SAE Form to the CRO within 24 h of observation or notification of a SAE. All of these events must also be recorded on the appropriate eCRF pages.

It is the responsibility of the Investigator to inform his or her local Institutional Review Board (IRB)/Ethics Committee (EC) about SAEs according to the local IRB/EC requirements. It is the responsibility of the Sponsor (or Sponsor's designee) to submit applicable SAE Reports to the Competent Authorities. Reporting of suspected unexpected serious adverse reactions (SUSARs) to the relevant IRB/EC, in accordance with the EU Clinical Trial Directive 2001/20/EC, the US Code of Federal Regulations 313.32 and ICH E6 Guidance on GCP and ICH E2A Guidance on Clinical Safety Management and all the applicable country regulations, will also be the responsibility of the Sponsor (or Sponsor's designee). [27, 29]

A safety contact sheet will be provided to the investigator and will be maintained in the investigator file at the site. Refer to the instructions and definitions for completing the SAE Form and for submitting all SAEs to the CRO.

7.1.4.1 Follow-up of Serious Adverse Events

For safety monitoring purpose, SAEs will be followed up by the Investigator until they are completely resolved or until a stable condition has been reached as no further improvement or change is expected according to conventional medical practice and according to the Investigator's judgment or until the patient is lost to follow-up. When the investigational site receives any information about a serious adverse event which changes or adds information to the initial investigational SAE form, the site will fill out a new investigational SAE form, tick the follow-up box and send the form via e-mail or fax within 24 h to the CRO, especially if this new information has an effect on the seriousness, relatedness or expectedness of an adverse event.

7.1.4.2 Adverse Events of Special Interest

Special attention will be paid to QT prolongation and constipation, in particular to severe forms of constipation (CTCAE grade 3 or 4 [28]). In such cases, an accurate follow up will be performed by the Sponsor.

7.1.5 Pregnancy Report

In the unlikely eventuality that a patient becomes pregnant during the trial, the Investigator will be requested to complete the Pregnancy Report Form and any relevant document. They must be forwarded to the CRO pharmacovigilance e-mail address or sent by fax (see Section General Information) within 24 h of becoming aware of the pregnancy. Even though pregnancy is not considered as SAE itself, pregnancy has to be reported within the timelines defined for SAE.

Pregnant patients, as well as partners of male patients who become pregnant during the study, will be followed by the Investigator and CRO / Sponsor until the fetus / newborn is delivered. Reports of Pregnancy Outcome will be sent by the sites directly to Helsinn Corporate Drug Safety. The patient's/partner's primary care physician (or obstetrician) will be requested by the Investigator to provide further information on the pregnancy outcome and to complete the Pregnancy Information Letter. If pregnancy occurs in a female patient between the screening and randomization phase, that patient will be removed from the study.

8 STATISTICS

This section summarizes the statistical principles and methods planned to analyze the data for this clinical study. The reference document is the ICH Topic E9 Statistical Principles for Clinical Trials: Note for Guidance on Statistical Principles in Clinical Trials [30].

Further details of the statistical analyses and data presentations to be used in reporting the study will be provided in the Statistical Analysis Plan (SAP), which will be finalized prior to data analysis.

8.1 Sample Size Determination

A total of 92 pediatric patients (i.e., 46 for each treatment group) will be enrolled in the study.

For each age class used for stratification, a sample size was computed. Each age class is powered to target a 95% confidence interval within 60% and 140% of the geometric mean estimate of clearance with at least 80% power.

The sample size was computed for the following age classes: Birth-<1 month, 1 <3 months, 3-<6 months, 6-<12 months, 1-<2 years, 2-<5 years, 5-<12 years, 12-<18 years.

Variability of clearance in each pediatric age class was estimated based on the same model used to determine the dose to be administered, which is:

$$Log(CL/F)p = log(CL/F)a + ADE * log(BWp/70)$$

where (CL/F)p and (CL/F)a are the systemic clearances in pediatric patients and adults, respectively, BWp is the body weight of children and ADE is an age-dependent exponent considered constant within each age class.

Variance of log (CL/F)p was then calculated as:

ADE² * Variance (log (BWp))

considering log (CL/F)a as a constant term.

Variance (log (BWp)) was obtained from published data in Fryar et al 2012 [31], where mean values in each age class and related standard errors were available.

Based on these data, the variance of log weight was obtained as:

Variance (BWp) = standard error $^2 * N$

and

Variance (log BWp) \approx Variance (BWp) / Mean²

(i.e., no assumption on the statistical distribution was made);

The table below reports the values as selected from published data in Fryar et al 2012 [31] and the further elaboration

Age class planned for the study	Age class [31]&	Weight (kg) N/ Mean / SE / gender [31]	ADE	Estimated SD (BWp)	Estimated SD (log BWp)	Estimated SD (log CL/F)
Birth to <1 month	Birth-2 months	82 / 5.0 / 0.11 / F	1.2	1.00	0.199	0.239
1 to <3 months	Birth-2 months	82 / 5.0 / 0.11 / F	1.2	1.00	0.199	0.239
3 to <6 months	3-5 months	111 / 7.1 / 0.11 / M	1	1.16	0.163	0.163
6 to <12 months	6-8 months 9-11 months	103 / 8.7 / 0.13 / M 108 / 9.6 / 0.15 / M *	1 1	1.32 1.56	ND 0.162	ND 0.162
1 to <2 years	1 year	297 / 10.9 / 0.10 / F	1	1.72	0.158	0.158
2 to <5 years	3 years	191 / 15.7 / 0.24 / F	0.9	3.32	0.211	0.190
5 to <12 years	9 years	191 / 36.6 / 1.17 / M	0.75	16.2	0.442	0.331
12 <18 years	17 years	188 / 77.4 / 2.41 / M	0.75	33.0	0.427	0.320

[&]amp; only data related to the age period actually used for the sample size calculations are reported in this table.

Sample size was then computed by the R program described in Wang et al 2012 [32] for each age class.

The resulted sample size for each treatment group, and the relevant power are provided in the table below:

Age class for the study	N estimated / dose	Power
Birth to < 1 month	6	0.891
1 to <3 months	6	0.891
3 to <6 months	4	0.832
6 to <12 months.	4	0.836
1 to <2 years	4	0.854
2 to <5 years	5	0.913
5 to <12 years	8	0.830
12 to <18 years	8	0.865

In order to facilitate the management of the study, the calculated sample size in the age class 2 to <5 years will be rounded up to 6 patients.

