1.3.2.4 Elimination

The apparent mean elimination half-life of netupitant generally ranged from 30 to approximately 100 h (for oral doses of 30 mg to 450 mg). There was a slightly supraproportional increase in C_{max} and AUC parameters for doses from 10 mg to 300 mg with dose proportional increases between 300 mg and 450 mg. No trends of CL or Vd changes were seen with increases in dose. [16]

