4.3 Dose and Administration

The netupitant doses to be tested in the pediatric population will match exposures to adult doses of 100 up to 300 mg as tested in pivotal Phase 2 trial NETU-07-07 [20], and 300 mg as tested in pivotal Phase 3 trials (NETU-08-08 [21] and NETU-10-29 [22]. These doses proved to be safe and effective. Basic assumption behind this choice is that efficacious netupitant AUC values in children are similar to those observed in adults at effective doses.

In order to predict the pediatric doses matching exposures to adult doses of 100 and 300, CL/F values in different age classes were estimated by pharmacokinetic allometry scaling according to the following model:

$$(CL/F)p = (CL/F)a * \left(\frac{BWp}{70}\right)^{ADE}$$

where (CL/F)p and (CL/F)a are the systemic clearances in pediatric patients and adults, respectively, BWp is the body weight of children, 70 is the standard adult BW expressed in kg, and ADE is an age-dependent exponent [24]. ADE values across the age classes were assumed to be the following [24]: 1.2 for children aged \leq 3 months, 1.0 for those aged \geq 3 months to 2 years, 0.9 for those aged \geq 2 years to 5 years, and 0.75 for those aged \geq 5 years. The model accounts for the effect of the body size change and organ maturation. An age-dependent exponent that decreases with the age increase, is consistent with a faster functional maturation occurring during the youngest age ranges.

Reference body weights for children were taken from growth charts compiled by the CDC (Centers for Disease Control and Prevention, Atlanta, GA, USA) [25].

Average AUC values in adults receiving 100 and 300 netupitant have been calculated by dividing these doses by the geometric mean of netupitant clearance in adults, (CL/F)a = 20.27 L/h, obtained from the population PK study (Study NETU-10-02 [26]), assuming linear kinetics. The netupitant doses for each pediatric age classes that are expected to yield these target AUC values have been calculated by multiplying AUCs by

the respective predicted CL/F in children, assuming the same netupitant oral bioavailability (F) in pediatric patients and adults.

In conclusion, netupitant doses per age class to be tested in the PK/PD-based dose finding study in pediatric patients resulted to be the following:

Age class	Dose 1 (mg/kg)	Dose 2 (mg/kg)
Birth to < 1 month	0.8	2.4
1 month to < 3 months	0.8	2.4
3 months to < 6 months	1.33	4
6 months to < 12 months	1.33	4
1 year to < 2 years	1.33	4

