8.3.4 Pharmacokinetic Analysis

Exploratory PK analyses will be applied to evaluate in the pediatric population the disposition characteristics of netupitant, its metabolites and palonosetron observed in adult patients. The initial population PK model (base model) will be developed by comparing structural models and random error models based on parameters such as the objective function values, the log-likelihood values, the Akaike's and the Bayesian's Information Criteria (AIC and BIC), the residual errors, the random distribution in conditional weighted residual plots, the graphical correlation between the observed versus predicted concentration values.

The final population PK model will include possible additional fixed effects represented by relevant covariates that will prove to correlate with one or more population PK parameters and contribute to significantly explain and minimize the inter-subject variability.

The final model will be qualified via a visual predictive check.

Inter-subject / inter-occasion variability (level 1 random-effect) and observation-level random error (level 2 random effect) will also be modeled.

Individual model-predicted PK parameter values will be estimated from the final population pharmacokinetic models, based on mean population parameter values (TVs) and on the individual random effect (η i). Individual plasma-concentration-time curves will be simulated from final model parameters, and secondary parameters such as C_{max} , t_{max} , AUC and $t_{1/2}$ estimated by non-compartmental methods.

Mean and coefficient of variation (CV) of the pharmacokinetic parameters will be calculated from the individual predictions.

The effect of continuous and categorical covariates on the PK parameter variability will be evaluated by step-wise forward addition and backward elimination procedures. Continuous covariates will include at least age, BW, albumin, total bilirubin, creatinine, ALT, AST, ALP. Categorical covariates will include at least gender, chemotherapy schedule, HEC/MEC, rescue medication (yes/no), concomitant medications.

Adult data from previous population PK study NETU-10-02 [26] after oral administration of the netupitant-palonosetron fixed combination will be used as prior information and included in the analysis.

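### The per-dose power figures in Protocol 8.1 count only body-weight variance in clearance, so the claim of at least 80% power is not supported

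*Protocol*

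**What the plan says.** Protocol 8.1 sets a precision target: "Each age class is powered to target a 95% confidence interval within 60% and 140% of the geometric mean estimate of clearance", with power of at least 80%. Clearance in children is modelled as adult CL/F scaled by weight with an age-dependent exponent (ADE) held constant within each class. The variance of log CL/F is then ADE² × Var(log BW), "considering log (CL/F)a as a constant term". Var(log BW) comes from published anthropometric data. The resulting SDs of log CL/F run from 0.158 to 0.331.

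The results are explicitly per dose: "The resulted sample size for each treatment group, and the relevant power are provided in the table below". N per dose is 6, 6, 4, 4, 4, 5, 8 and 8 from the youngest to the oldest class, with the 5 rounded up to 6, giving 46 per group and 92 in all.

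Three other places bear on this:

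- Protocol 8.3.4: "Inter-subject / inter-occasion variability (level 1 random-effect) and observation-level random error (level 2 random effect) will also be modeled". It also plans to test covariates other than weight: "Continuous covariates will include at least age, BW, albumin, total bilirubin, creatinine, ALT, AST, ALP".
- Protocol 4.3 gives adult CL/F as a geometric mean of 20.27 L/h, "obtained from the population PK study (Study NETU-10-02 [26]), assuming linear kinetics". No CV is given.
- Protocol 1.3.2.4 is mixed on dose dependence. It reports for Cmax and AUC that "There was a slightly supraproportional increase" between 10 and 300 mg, and also that "No trends of CL or Vd changes were seen with increases in dose".

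**The concern.** Treating the adult term as a constant removes every source of between-child variation in clearance except weight. The analysis section expects such variation, and a geometric mean from a population PK study summarises a distribution. Any non-zero weight-independent variance lowers every power in the table.

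This calculation, plus one rounding step, is the only stated justification for the number per class and for the total of 92. A reader would take it that four children per dose give more than 83% power to reach the precision target.

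**Working it through.** **Inputs from Protocol 8.1.** SD of log CL/F by class: 0.239, 0.239, 0.163, 0.162, 0.158, 0.190, 0.331, 0.320. N per dose as above. Limits 60% and 140%; the upper limit binds because ln 1.4 = 0.336 is smaller than −ln 0.6 = 0.511.

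**Formula.** The interval meets the target when t × s/√m ≤ ln 1.4, so

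Power = P[χ²(df) ≤ df × m × (ln 1.4)² / (t²(0.975, df) × SD²)].

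Per dose, m = n and df = n − 1. Pooled over the two doses, m = 2n, with df = 2n − 1 without a dose term and 2n − 2 with one.

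**Step 1: reproduce the protocol.** Example, 3 to <6 months: n = 4, t = 3.182, SD = 0.163. The bound is 3 × 4 × 0.336² / (3.182² × 0.163²) = 5.05, and P[χ²(3) ≤ 5.05] = 0.832, as tabulated. All eight classes give 0.891, 0.891, 0.832, 0.836, 0.854, 0.913 (n = 5), 0.830 and 0.865, which match to three decimals. At the planned n = 6, the 2 to <5 years class gives 0.986. The arithmetic is right, and the match shows that no other variance entered.

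**Step 2: add weight-independent variability.** Let ω² = ln(1 + CV²) and SD² = (table SD)² + ω². The protocol gives no netupitant CV, so the CV columns are assumptions. The break-even column needs no assumed CV.

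| Age class | n per dose | Largest CV keeping 80% | Power, CV 10% | CV 20% | CV 30% | CV 40% |
|---|---|---|---|---|---|---|
| Birth to <1 mo | 6 | 11.6% | 0.82 | 0.62 | 0.39 | 0.22 |
| 1 to <3 mo | 6 | 11.6% | 0.82 | 0.62 | 0.39 | 0.22 |
| 3 to <6 mo | 4 | 4.8% | 0.70 | 0.44 | 0.245 | 0.14 |
| 6 to <12 mo | 4 | 5.2% | 0.71 | 0.44 | 0.245 | 0.14 |
| 1 to <2 y | 4 | 6.3% | 0.72 | 0.45 | 0.25 | 0.14 |
| 2 to <5 y | 6 | 18.7% | 0.95 | 0.77 | 0.48 | 0.27 |
| 5 to <12 y | 8 | 7.8% | 0.78 | 0.63 | 0.44 | 0.27 |
| 12 to <18 y | 8 | 11.6% | 0.82 | 0.67 | 0.46 | 0.28 |

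Example, 3 to <6 months at CV 20%: ω = 0.198, SD = √(0.163² + 0.198²) = 0.256, the bound falls to 2.04 and power to 0.44.

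**Step 3: other readings of the target.** If the target is weight-adjusted clearance, SD = ω alone. Largest CV keeping 80%:

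| Target | n = 4 | n = 6 | n = 8 |
|---|---|---|---|
| Weight-adjusted, per dose | 17.1% | 27.0% | 35.0% |
| Weight-adjusted, pooled, dose term | 33.4% | 47.5% | 59.6% |
| Weight-adjusted, pooled, no dose term | 35.0% | 48.4% | 60.3% |

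Weight-adjusted pooled power with a dose term, for n = 4/6/8, is 0.90/1.00/1.00 at CV 30%, 0.59/0.95/1.00 at 40% and 0.33/0.73/0.96 at 50%. A simulation at CV 30% and 40% agrees (n = 4: 0.898 and 0.590).

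Pooled but not weight-adjusted, power across classes is 0.97–1.00 at CV 20% and 0.77–0.99 at CV 30% with a dose term (0.98–1.00 and 0.81–0.99 without). In this reading the n = 4 classes hold 80% up to about 29% with a dose term and 30.5% without.

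**The case against.** The simplification is disclosed, and the powers follow exactly from it. The protocol gives no netupitant CV, so the true shortfall is unknown. The table SDs for the two oldest classes (0.331 and 0.320) already amount to a total CV of about 33–34%, so total variability there may not be understated. The planned analysis is one population PK model with weight as a covariate and adult data as prior information, which is closer to the pooled, weight-adjusted case. The primary endpoint is the exposure–response relation, not clearance precision per class and dose. On this view a single sentence saying that the powers reflect weight variability only would be enough.

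Much of this stands, but it limits the consequence and does not rescue the table. Disclosing a formula is not the same as saying that the stated power depends on zero residual variability, and 8.1 does not say that. The table is per dose, so pooled figures support a different claim. If weight is adjusted for, the component that 8.1 counts is largely removed and the one it omits remains. The size is indeed unknown, which is why the break-even CVs are the firmest result. A caveat alone would leave the sample size with no power figure that allows for between-child variability.

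**Conclusion.** The point holds. The claim of at least 80% power per dose is true only if weight-independent variability in clearance is at or below 4.8–18.7%, depending on class. At an assumed CV of 10%, four of the eight classes fall below 80%; at 20%, all eight do.

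The consequence is bounded. No test or decision rule uses the 60–140% interval, and nothing here shows that the final population PK estimates will be imprecise. Weight-adjusted and pooled over doses, the n = 6 and n = 8 classes may well reach 80%. The three n = 4 classes (3 months to <2 years) are the most exposed in every reading. Precision borrowed from the adult data is not counted in any of these figures. The statement should be corrected, but the design need not change.

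**What to change.** In Protocol 8.1, name the target and use the matching variance:

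- Unadjusted CL/F: ADE² × Var(log BW) + ω².
- Weight-adjusted CL/F: ω² alone.

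Here ω is the between-subject SD of log CL/F that remains after weight adjustment, taken from NETU-10-02. Check that the ω reported there excludes weight, otherwise weight is counted twice. Show a CV range as well, because an adult value need not hold in infants.

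Then either (a) restate the per-dose power table, or (b) state the precision target per age class pooled over both doses, with and without a dose term, since Protocol 1.3.2.4 points both ways on dose dependence. Report the power obtained, and drop the 80% claim where it is not reached.

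The cost is one recalculation and a rewording. No patients are added, and analysis, randomization and dosing stay as they are. The stated power becomes less favourable. Option (b) gives up the per-dose claim and still does not secure 80% in the n = 4 classes above a CV of about 33–35% (weight-adjusted) or 29–30.5% (unadjusted). Keeping 80% per dose for unadjusted CL/F would need 8 + 8 + 6 + 6 + 6 + 7 + 10 + 10 = 61 patients per dose at CV 20%, or 10 + 10 + 8 + 8 + 8 + 9 + 12 + 12 = 77 at CV 30%, against 46 planned. That increase is not proposed.

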8.2 Definition of Study Populations for Analysis

The following analysis populations are defined:

^{*} given that mean values were very similar, data from the class with the larger SD of weights was used

ADE = age-dependent exponent; BWp= body weight of children; CL/F= systemic clearance; F= Female; M = Male; ND= Not Done; SD = Standard Deviation

The **Full Analysis Set** (FAS) includes all patients randomized or to whom a study drug was assigned and who received a HEC or MEC regimen and the entire planned volume of netupitant and palonosetron. Following the intent-to-treat principle, patients will be assigned to the treatment group according to the treatment assigned/randomized. FAS will be used for demography, other baseline characteristics and efficacy analyses.

The **PK population** includes all patients who received the entire planned volume of netupitant and/or the entire planned volume of palonosetron and who have at least one measurable concentration of netupitant and/or palonosetron. PK population will be used for all PK analyses.

The **Safety** population includes all patients who received at least part of the planned volume of netupitant or at least part of the planned volume of palonosetron. Patients will be assigned to treatment groups according to the actual treatment received. Safety population will be used for demography, other baseline characteristics and for all safety analyses.

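### Section 8.1 gives the 2-<5, 5-<12 and 12-<18 year classes the weight spread of one year of age, so their stated powers leave out growth across the class; the effect is material only for 5-<12 years

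*Protocol*

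**What the plan says.** Protocol Section 8.1 sets the precision target class by class: "For each age class used for stratification, a sample size was computed", and each class is to "target a 95% confidence interval within 60% and 140% of the geometric mean estimate of clearance with at least 80% power".

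The variance of log clearance is taken as ADE² × Var(log BWp), "considering log (CL/F)a as a constant term". ADE is the age-dependent exponent and BWp the body weight of the children. Weight spread is therefore the only source of variance in the calculation. It comes from published anthropometric data, "where mean values in each age class and related standard errors were available", with SD = SE × √N and SD(log BWp) ≈ SD / mean.

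The weight table shows one single-year, single-sex row for each of the three oldest classes:

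- 2-<5 years: 3-year-old girls, "191 / 15.7 / 0.24 / F" (N / mean / SE / sex)
- 5-<12 years: 9-year-old boys, "191 / 36.6 / 1.17 / M"
- 12-<18 years: 17-year-old boys, N 188, mean 77.4 kg, SE 2.41

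The only reason given for letting a narrower age band stand for a class is the table footnote for 6-<12 months: "given that mean values were very similar, data from the class with the larger SD of weights was used".

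The power table then gives 0.913 (5 per dose), 0.830 (8 per dose) and 0.865 (8 per dose) for the three oldest classes. The 2-<5 class is rounded up to 6 per dose for study management.

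**The concern.** The formula needs the variance of log weight among the children in the class. For a class spanning several years, that is the average within-year variance plus the variance of the yearly mean log weights. A single-year row supplies an estimate of the first part only.

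In most of the younger classes the source row spans the class, so growth is already inside its SD. In the 6-<12 month class the omission is argued from similar means (8.7 and 9.6 kg). That argument cannot carry over to the older classes: the printed means are 15.7 kg at 3 years, 36.6 kg at 9 and 77.4 kg at 17.

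At stake is the protocol's statement that every age class reaches at least 80% power for its clearance precision target. The question here is how the weight spread is derived. Clearance variability between children of equal weight is a separate matter.

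**Working it through.** **1. Reproducing the printed powers.** The upper limit binds on the log scale, ln 1.4 = 0.3365. With n patients per dose, power is the probability that t(0.975, n−1) × s / √n does not exceed 0.3365. This equals the chi-square CDF on n−1 df at (n−1) × [0.3365 × √n / (t × SD)]², where SD = ADE × SE × √N / mean.

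For 5-<12 years:

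- SD(BW) = 1.17 × √191 = 16.17; SD(log BW) = 16.17 / 36.6 = 0.442; SD(log CL/F) = 0.75 × 0.442 = 0.331.
- With n = 8 and t = 2.365, the argument is 7 × (0.4025 / 0.3313)² = 10.33, and power = 0.829 (0.830 with the rounded SD).

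| Class | n per dose | Stated | Reproduced |
|---|---|---|---|
| Birth-<1 and 1-<3 months | 6 | 0.891 | 0.891 |
| 3-<6 months | 4 | 0.832 | 0.831 |
| 6-<12 months | 4 | 0.836 | 0.835 |
| 1-<2 years | 4 | 0.854 | 0.853 |
| 2-<5 years | 5 | 0.913 | 0.913 |
| 5-<12 years | 8 | 0.830 | 0.829 |
| 12-<18 years | 8 | 0.865 | 0.864 |

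All agree within 0.002. The stated powers of the three oldest classes therefore rest on single-year spread alone.

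**2. Adding growth.** SD(log CL/F) = ADE × √(within-year SD² + growth SD²). Assumptions, none of them in the protocol:

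- ages are uniform within the class;
- mean weights are interpolated (linearly or log-linearly, at whole- or mid-year ages) through the printed 10.9, 15.7, 36.6 and 77.4 kg at 1, 3, 9 and 17 years;
- the printed row's SD(log BW) holds in every year of the class.

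| Class | Growth SD (log BW) | SD(log CL/F) | Power | Stated |
|---|---|---|---|---|
| 5-<12, n = 8 | 0.235-0.258 | 0.375-0.384 | 0.64-0.67 | 0.830 |
| 12-<18, n = 8 | 0.133-0.162 | 0.335-0.342 | 0.79-0.82 | 0.865 |
| 2-<5, n = 5 (tabulated) | 0.132-0.159 | 0.224-0.238 | 0.73-0.79 | 0.913 |
| 2-<5, n = 6 (planned) | 0.132-0.159 | 0.224-0.238 | about 0.90-0.93 | not given |

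Example for 5-<12 years with growth SD 0.240: 0.75 × √(0.442² + 0.240²) = 0.377, and power = 0.665.

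**3. Cruder growth assumptions, 5-<12 years.** With one constant log-growth rate, growth SD = rate × 7 / √12.

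- Rate from 3 to 9 years, ln(36.6/15.7)/6 = 0.141 per year: growth SD 0.285, power 0.60.
- Rate from 3 to 17 years, ln(77.4/15.7)/14 = 0.114: growth SD 0.230, power 0.68.
- Rate from 9 to 17 years, ln(77.4/36.6)/8 = 0.0936: growth SD 0.189, power 0.73.

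**4. How much growth the plan's own SD can absorb.** At n = 8, 80% power requires SD(log CL/F) of at most 0.340, that is SD(log BW) of at most 0.340 / 0.75 = 0.453. With 0.442 already used, the room left is √(0.453² − 0.442²), about 0.10. Under uniform ages that is a rise in mean weight of about 42% from 5 to 12 years. Even the slowest rate above gives exp(7 × 0.0936) = 1.93, a rise of about 93%.

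**5. Sensitivity to the within-year SD.** With growth SD 0.235-0.258, the 5-<12 class keeps 80% if the average within-year SD(log BW) is at most √(0.453² − growth SD²), about 0.37-0.39. At 0.35 its power would be about 0.85-0.88. The 12-<18 class needs at most about 0.42-0.43, against the 0.427 used.

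**The case against.** The strongest reply is that the 9-year row may already be generous. The chosen rows switch sex between classes and are not central (17 is the last year of 12-<18). The one selection rule in print, the 6-<12 month footnote, takes the row with the larger SD. If 0.442 is near the largest yearly SD in 5-<12, adding full growth variance to it overstates the class spread, and step 5 shows that the result can reverse. This stands as a limit on the size of the effect. It does not rescue the stated power: the protocol does not state that rule for the older classes, does not call the 9-year row an upper bound, and does not give the other years' SDs.

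A second reply is that Section 8.3.4 plans a population PK model with age and weight as covariates and adult data included, and that 16 patients per class pooled over doses would give power above 0.999 even with the growth term. That lowers the practical consequence. It does not validate the figure, because Section 8.1 states its power per dose group: "The resulted sample size for each treatment group, and the relevant power are provided in the table below". Nor can weight be adjusted out selectively. It is the only variance in the calculation, so spread within a year cannot count while spread between years does not.

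A reader might also infer that all three classes miss the target. The figures do not support that. The 2-<5 shortfall concerns 5 per dose, which will not be enrolled, and the 12-<18 range straddles 80%.

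**Conclusion.** The point holds. The growth term required by the plan's own formula is missing for the three multi-year classes, so the powers stated for them are not those of the class. The consequence is material only for 5-<12 years: about 0.64-0.67 at 8 per dose (0.60-0.73 under cruder growth assumptions), against 0.830 stated. This rests on interpolated means from rows of mixed sex, a uniform age mix, and 0.442 as the SD in every year. The 12-<18 class loses its margin, and the 2-<5 class is safe at the planned 6 per dose.

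A reader might go further and take about 0.65 as the true power on the plan's own figures, or conclude that 8 per dose is shown to be too few. The protocol prints only one mean weight inside 5-<12 years and no other within-year SD, so it supports neither. What is established is that the stated 0.830 omits a component of variance, and that 80% is met only if the average within-year SD is clearly below the value the plan used.

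**What to change.** In Section 8.1, compute SD(log BWp) for each multi-year class as the square root of (mean within-year variance of log weight + variance of the yearly mean log weights), using every year of the class from the table already cited. Restate the power at the planned 6, 8 and 8 per dose, and keep the claim of at least 80% power only for the classes that reach it.

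The cost is a short recalculation and a wording change. A stated power may become less favourable. No change in enrolment is needed.
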